Health Technology Assessment Programme

NIHR HTA Programme

23 August 2012

[contact]

[contact] web: www.hta.ac.uk

email: [contact]

POWER Positive Online Weight management in Routine care

Sponsor: University of Southampton

Chief Investigator:

[name]
Prof of Primary Care Research
Community Clinical Sciences Division
University of Southampton
Aldermoor Health Centre
[name]
Southampton
Hants
[name]

[contact] [name]

Research Objectives:

To estimate the effectiveness and cost-effectiveness of a) an internet based behavioural intervention with face to face support as needed and b) an internet behavioural intervention with minimal face to face support among obese patients in primary care.

Design Summary.

This study is in two phases:

- 1) Phase I (12 months): research governance arrangements will be finalised, practices recruited and trained in study procedures and intervention, the development of the website will be extended to address maintenance issues, and testing will take place to ensure the full trial protocol works seamlessly.
- 2) Phase II. A randomised trial will compare management using a) web intervention with nurse support; b) web intervention with minimal nurse support; c) brief structured advice and follow up for weighing.

Methods:

Phase 1 (0-12 months): further development of the website for maintenance and relapse.

Development of support for weight maintenance. Regular self-monitoring of weight and rapid action to correct relapse is crucial to weight maintenance, and so we will create a series of 24 brief (2 page) maintenance-oriented web-based sessions with novel and interesting content and links to encourage patients to continue to use the website to track their weight at least bi-weekly (preferably weekly); similar content has recently been successful in achieving 65% adherence at 28 months without face-to-face support ¹². After mandatory weight entry patients will receive tailored feedback giving encouragement and virtual rewards if maintaining weight loss (e.g. reminders of health benefits accrued; 'achiever class' awards, with emails notifying nominated support people of achievements, including nurse). Weight gain will trigger initial referral to an automated 'recovery package' including reminders, personalised messages preset by the patient and new advice concerning appropriate goal-setting, boosting motivation, planning for and recovering from difficult times (e.g. holidays), overcoming difficulties etc. Weight gain on two consecutive logins will trigger nurse input (if randomised to receive this). Failure to login for more than 2 weeks will trigger automated reminders and motivating messages.

Patient Interviews

Intensive qualitative piloting will be carried out to ensure that these new web-based sessions are accessible and engaging, and to inform modification of them as necessary. For this purpose we will use a panel of over 30 people recruited for piloting the weight loss intervention; these will be participants who indicated on their consent form that they would be prepared to be approached. Face-to-face 'think-aloud' sessions¹³, **and telephone interviews** will be used to elicit and observe immediate responses to every aspect of each session. Users will be invited to use the website for consecutive weeks and months while keeping a semi-structured diary recording their reactions and experiences; diary data will be analysed and participants interviewed retrospectively about their experiences over this period. Thematic analysis ¹⁴ will be employed to identify common reactions to the website and experiences of the intervention and inform iterative modification. This process will be continued until no significant modifications to the website appear to be required.

Healthcare professional process interviews

Following the completion of all nurse support appointments, practice staff with experience of recruiting and/or supporting patients recruited to the study will be invited to take part in an interview in order to understand their experiences of delivering the study and working with patients in the study. Views about the website and the study procedures will be sought in order to improve our understanding of the deployment of the programme within primary care and inform future programme development.

Phase 2. RCT

Inclusion criteria. Adult patients with BMI >=30 (or 28 with hypertension or hypercholesterolaemia) documented in the GP case records¹² will be eligible.

Exclusions: Current major mental problems e.g. psychosis (difficulty completing outcomes); very ill or unable to change diet (e.g. severe LVF); pregnancy, or breast feeding; perceived inability to walk 100 metres (physical activity difficult).

Invitation of patients/recruitment. Up to 100 patients in each practice will be randomly chosen from GP electronic records, and invited by letter to a screening appointment to confirm eligibility; with 15-20 patients per practice being recruited to the trial. Patients can also be referred opportunistically when seen in practice nurse or GP clinics. Recruitment will take place over 6 months in up to 44 practices from the South West and South East Hubs of the PCRN.

Randomisation and informed consent. At the screening appointment the practice nurse will take written, informed consent and the patients' details in each practice will be sent to an external randomisation line to allow stratification of randomisation - gender; waist (>102 cm men; >88cm women); BMI >=35; Index of material deprivation score (>median); partner in the household; source of patients (invited by mailing or opportunistically invited). Practice staff will inform patients of their group indicating the nature and timing of contacts (and with the personalised website password as appropriate in the web group).

Planned interventions

1) Control: Very brief advice and follow-up. The practice nurse will provide brief structured advice (less then 5 minutes) about a healthy diet (healthy food swaps) and physical activity (advice to take 30 minutes of moderate intensity exercise per day) using brief written materials. For follow-up, nurses will arrange very brief follow-up (5 minute appointment) with sufficient time for measurement of weight only at 6 months and 12 months. Nurses will not have time to perform counselling, and will also actively be instructed to provide supportive comments only and not to engage in active behavioural intervention over and above the brief structured advice.

- **2) Web intervention with nurse support**. The aim in this group is to provide a more intensive evidence-based intervention, but which should require less than half the time of traditional face to face evidence-based lifestyle interventions. The intervention components are as follows:
 - Physical activity. Diet and physical activity targets supported by drug treatment as necessary are based on NICE guidance. Participants will be given targets of at least 2.5 hours of moderate intensity physical activity per week (brisk walking), and, where walking is the preferred physical activity, will be encouraged, where possible, to aim for at least 10,000 steps per day supported by pedometers⁴⁰. Observational studies suggesting 1500-2000 Kcal per week may be required to maintain weight loss and thus a flexible approach will be used to increase the target amount of physical activity if necessary⁷.
 - Diet. Participants will be given the choice of either low calorie or low carbohydrate approaches (based on a strong preference expressed in the pilot phase by patients for a choice of dietary approaches). These eating plans are intended to achieve a sustainable rate of weight loss of 0.5-1Kg a week ¹⁷; a graded approach to negotiating more demanding dietary targets will be used if no weight loss is occurring. Patients who have succeeded in losing 5% of body weight will be given the choice of continuing to pursue gradual weight loss or attempting to maintain this weight loss.

 Low Calorie eating plan: the website provides a choice of dietary behavioural components (e.g. portion size, food swaps, calorie counting, meal spacing etc) to achieve a 600Kcal deficit diet¹⁸; Low carbohydrate eating plan: this will consist of an induction phase (<50g carbohydrate) for 2 weeks, followed by targets intended to produce ongoing weight loss (50-80g carbohydrate). This low carbohydrate eating plan differs from current commercial diets (e.g. Atkins) in ensuring at least 5 fruit and vegetable portions after the first 2 weeks.

 - Web-based self management. Key principles adopted for development of our intervention were that it should a) be theory- and evidence-based⁴. b) be accessible and engaging, c) should offer users who have become sceptical about the efficacy of diets a novel, empowering self-management approach ^{9;19}, d) have a positive, sustainable focus on forming flexible healthy eating and physical activity habits rather than prescribing restrictive, complex, or intrusive regimes 9,10;17;18 e) be fully integrated with the nurse support (for those receiving it), f) take a graded approach to target-setting, ensuring the patient experiences early success in achieving goals ^{17;21}. Using the MRC-recommended approach to developing complex interventions ²², key evidence-based elements and behaviour change techniques²³ we have identified for inclusion are: goal-setting, planning and self-monitoring^{23;24}, techniques to enhance motivation and self-confidence^{1;2} self-defeating cognitions²⁵ and create an environment that reduces cues to unhealthy eating and prompts and rewards healthy eating and physical activity ^{26;27}, 'success stories' and evidence summaries that demonstrate how these techniques have been used by others to overcome barriers to weight loss²¹; a discussion board with expert feedback from the nurse ^{3;28}, and email and text reminders ^{22;28}. In the introductory orientation session the patient chooses their eating plan and initial personal goals and logs their weight. The first and all subsequent sessions conclude with an index of recommended, trustworthy links to relevant further web resources (e.g. on NHS Choices), including meal swap plans, calorie counters, motivating videos of success stories etc. All subsequent sessions commence with asking the patient their weight and whether they achieved the goals set the previous week, and then give feedback tailored to their progress (e.g. achieved goals but did not lose weight triggers pages on setting more demanding goals; did not achieve goals or lose weight triggers pages on increasing motivation, overcoming barriers or choosing different goals). The second session, after providing feedback relevant to progress during the first week, focuses on obtaining support from family and friends, the website (including setting personalised email and text message reminders) and the nurse. The third session offers a choice between a webbased adaptation of a well-validated primary care intervention to promote regular walking¹

- reinforced by pedometer use⁸, or setting personal physical activity goals. The patient can select all subsequent weight loss sessions from a menu which includes coverage of healthy drinking patterns, relapse prevention, and coping with cravings, stress-induced eating, busy times and social pressures.
- Nurse support. Very brief appointments for weight measurement at 6 months and 12 months (final follow-up) will occur as in the control group. In addition all patients will be offered brief face to face behavioural assessments at 2 weeks, 6 weeks, and 3 months. If a rate of weight loss equivalent to 5% weight loss over 6 months is not being achieved or maintained which we anticipate could be up to half the cohort face to face appointments will be made, up to a maximum of 4 more appointments in total in the first year (which is half the number of the average face to face appointments for dietary and behavioural counselling from trials documented in the NICE review⁵). In line with NICE guidance⁵ if 5% weight loss in not achieved Orlistat will be offered; it will be stopped according to standard stopping rules ⁵. Orlistat can also be used for weight maintenance⁵. The purpose of the nurse contacts is to provide reinforcement, and also to be able to help patients address ongoing or new issues where the web has provided limited support. Where issues arise the approach will be to encourage patients to find their own solutions to the problems raised.
- Other features. Based on previous evidence from systematic review of particular strategies to encourage maintenance of weight loss¹¹, patients will asked to participate in web based peer interaction, and to involve the family or spouse to help limit weight regain.
- **3) Web intervention with minimal face to face support.** This group aims to provide a very brief intervention with minimal face to face contact time which therefore could be applied more rapidly and extensively in the NHS. Patients will work through the website, will be prompted to use it regularly by email, and brief face to face contact for weighing only at 6 and 12 months as in the control group. In addition this group will have a brief (10 min) face to face consultation at 2 weeks to confirm the physical activity and dietary targets, 3 brief online contacts at 1, 2, and 3 months and up to 2 further telephone contacts (i.e. 3 brief additional personal contacts compared with the control group until final follow-up) for patients not losing 5% of weight.

Support and training for Nurses. We have shown in piloting that nurses can learn to use the structured intervention materials both easily (i.e. requiring relatively little training) and effectively. The web pages for nurses a) provide a brief overview of the rationale, philosophy and structure of the intervention, b) provide a structured guide to the content of each patient support session c) give nurses access to an overview of their patients' progress and the content of each session, and d) send email reminders and notifications to nurses when patient support sessions are required (at timed intervals and if patient not using website or not losing weight), and include a tick-box record for nurses to complete logging what support has been provided.

Proposed time period for retention of relevant trial documentation

Trial documentation will be kept for 15 years.

Proposed outcomes/data collection (at baseline and unless specified at 6 and 12 months). Primary outcome measure:

Weight (primary outcome): lightly clothed, without shoes, at the same time each day, and using automated Tanita digital scales (which will also allow measurement of body composition).

Secondary outcome measures:

Food and drink consumption and physical activity (at baseline and final follow-up): These behavioural measures (and intentions/attitudes to behaviour – see below) will be made in the intervention group at baseline and follow-up but in the control group only at final follow-up to avoid

such measurement being a prompt for behaviour change in the control group.

Physical activity: Using the validated Godin leisure time physical activity questionnaire and physical activity monitors^{29,30}. Activity monitors have well documented limitations in validity, although may provide an adequate proxy to estimate between group differences. One third of the sample will in addition be randomised to wear the Actiheart monitors which will allow much more precise estimation of physical activity.

Food and drink consumption: Using validated brief FFQs for major food groups and also alcohol developed by our group for use in primary care. ^{31,32}

Indices of the metabolic syndrome (waist,BP,glucose,TG,HDL)³³⁻³⁶. Individuals with the metabolic syndrome are at particular risk. We will report the number (%) in each group using a definition of 3 out of 5 of high measurements³⁷, and a continuous outcome based on the mean z score for each individual (or mean rank as appropriate) - supported by empirical evidence of a close factor structure among the variables³⁸;

Waist: nurses will measure waist midway between the lower ribs and the iliac crests³⁹ also height, hip, skin fold thickness – to allow estimation of BMI, waist hip ratio, and fat mass ^{40; 41}

Blood pressure (BP) 42: Measured 3 times (after 5 min) using a validated OMRON 43;44;

Serum measures: Liver function tests (particularly to monitor non alcoholic fatty liver disease), fasting serum cholesterol/HDL/LDL/triglyceride (TG) ^{41,45,46} ⁴⁷ glucose, HbA1c and insulin ^{48,49} (which would be expected to be modified by weight reduction); also ferritin (important to measure due to reducing cereals (a key source of iron) in the low carbohydrate diet)

Patient satisfaction and understanding. Simple Likert scale responses are reliable and valid.⁵⁹; **SF36**⁵⁰: The eight scales have been shown to be valid in a wide range of conditions in primary care; **EuroQol**^{51;52} (EQ-5D): the EuroQol provides a measure of quality of life for economic analysis;

Psychological status: Using the Hospital Anxiety and Depression scale⁵⁰ and brief state anxiety.⁵³ Obesity is associated with psychological morbidity,⁵⁴ and distress, anxiety and depression may be changed by physical activity⁵⁵;

Adherence and predictors of adherence. We will measure intention to change behaviour for each specific behaviour, and other items based on components of the TPB⁵⁶ (attitudes, social norms, perceived behavioural control) ^{2;15;16} ⁵⁶. We will measure behavioural adherence through self report which is likely to strongly predict weight loss³⁵. All website usage is automatically recorded, including frequency and duration of logins, options selected and all data inputted (e.g. weekly goal achievement).

Outcome measurement: At the appointments with the practice nurse (baseline, 6 months, 12 months), the physiological measurements will be performed, and patients weighed; research staff blind to group will also perform a final weight measurement at 12 months. For the few patients who do not provide questionnaire answers we will perform up to 2 emails/mailings, and telephone follow-up of those still not responding.

Socio-Demographic data. Age, gender, education, internet experience, social deprivation indices based on post code will be recorded.

Notes review. All patient's notes will be reviewed to document consultations, returns, time to return, reasons for returns, complications, economic data and any subsequent referrals. ⁵⁷

Sample size. We wish to compare each of the intervention groups primarily with control but also with each other so for our primary outcome (weight) we allow for alpha=0.017 (i.e. 0.05/3) to minimise type I error. For a standardised effect size of 0.33 (i.e. a small effect size, equivalent to 2-3 Kg difference assuming an SD of change of 6.5-7.5 Kg^{6,48}) and 80% power this requires 174 patients per group with complete data, or 654 patients in total allowing for 20% loss to follow-up (hence we will aim to recruit a minimum of 660 patients).

Analyses

Primary analysis: Repeated measures ANOVA for the principal continuous outcomes (i.e. weight) between groups and for the secondary outcomes, controlling for stratification variables.

Subgroup analyses: Estimates of effect in subgroups according to baseline waist measurement (high vs low waist), and the presence of the metabolic syndrome (syndrome vs no syndrome) will be explored. Assessments will be made of outcomes (weight, reported behaviour change, measured behaviour change) according to website usage and changes in psychological variables (e.g. change in components of the TPB) and according to the type of diet chosen by patients. **Other analyses:** Weight changes will be plotted against changes in metabolic variables to compare slopes between groups.

The most conservative intention to treat analysis will assume that those patients lost to follow-up have regained their initial weight, with an adjustment to allow for the variance (if exactly the same measurements were used there would be no variance of change for the missing data, and so would underestimate the overall variance of change). The study will be reported in accordance with the CONSORT (Consolidated Standards of Reporting Trials) statement.

Economic analysis. The cost of intervention and follow-up related service use, including the time taken to train staff, surgery attendance, admissions and referrals, will be collected in the trial. Resource use data will be collected by notes review, GP and nurse documentation (e.g. of consultation time) and patient self-report.

Qualitative process analysis: During months 18 to 24 of the study we will interview 12-16 patients from both the intervention groups immediately after the 12 month appointment, purposively sampling for diversity in baseline characteristics (age, gender, internet experience), adherence levels and outcomes. Interviews will be tape-recorded, fully transcribed and analysed by thematic analysis ¹⁴ with constant comparison⁵⁸ of emerging themes based on intervention group and all the factors used for purposive sampling. The aim will be to identify processes that may have influenced intervention acceptability and effectiveness for different patients.

Risk and benefits for trial participants

Since the study will use recommended strategies there should be no risk to participants. Major complications are unlikely in this sample. Given the structured advice to patients – probably better information than is normally available in routine care - the standard of care in the control group is likely to be higher than routine practice since most patients with obesity currently get little or no help either in weight loss or weight maintenance.

Project timetable.

0-12 months secure local approvals; approach recruit and train practices; prepare practices for recruitment including preparing list of patient and letters; perform ongoing qualitative work with existing pilot sample; pilot the website to address maintenance.

12 months - 18 months recruit patients for main trial

18 to 30 months follow-up patients from main trial

30 to 36 months complete data collection, cleaning, analysis and report writing

Reference List

- (5) Obesity guideline development group. National Institute for Health and Clinical Excellence: Obesity full guideline. Nice org 2006; http://guidance.nice.org.uk/CG43/guidance.

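### Nothing stops two people from one household being randomised to different arms, so a control may be partly exposed to the web intervention at home

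*Protocol*

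**What the plan says.** **Entry.** Under Invitation of patients/recruitment, "Up to 100 patients in each practice will be randomly chosen from GP electronic records", with 15-20 recruits expected per practice. The same paragraph opens the second route: "Patients can also be referred opportunistically when seen in practice nurse or GP clinics". The Exclusions cover major mental problems, being very ill or unable to change diet, and finally "pregnancy, or breast feeding; perceived inability to walk 100 metres (physical activity difficult". None concerns another household member.

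**Allocation.** Under Randomisation and informed consent, "patients' details in each practice will be sent to an external randomisation line to allow stratification of randomisation - gender". The unit is the patient. The list of factors ends with "partner in the household; source of patients (invited by mailing or opportunistically invited".

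**Household content of the intervention.** Under Web-based self management, the second session "focuses on obtaining support from family and friends", and the list continues with the website and the nurse. Under Other features, in the description of the web plus nurse arm, patients are asked "and to involve the family or spouse to help limit weight regain". The minimal-support arm works through the website too, but its description does not repeat the request about the spouse.

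**Protection of the control arm.** Nurses are told not to give controls active behavioural intervention beyond the brief advice. Behavioural questionnaires are withheld from controls until final follow-up so that measurement does not prompt change. Website access is by personalised password. No section deals with exposure inside a household.

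**The concern.** Two people at one address can both be eligible, enter by either route, and be allocated to different arms. If one is a control and the other is in a web arm, the web patient may bring changed meals, activity goals and printed or on-screen material into the shared home, and part of the intervention is designed to draw the household in. The control then receives some of what the trial is testing.

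This would mainly shrink the two web-versus-control differences, which are the primary comparisons. It cannot be undone after the trial, and unless household links are recorded nobody can identify the affected pairs. The protocol gives up baseline behavioural data in controls to avoid a questionnaire prompt, so leaving a plausible prompt at home unaddressed sits oddly with its own approach.

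**Working it through.** **Inputs from the protocol (Sample size).** Standardised effect 0.33; alpha 0.017; 80% power; 174 per group with complete data; 20% loss; 654 in total, with a minimum of 660 to be recruited. Equal group sizes imply 1:1:1 allocation. Sidedness is not stated; two-sided is assumed.

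**The plan's own figure.** The loss step reproduces: 174 / 0.8 = 217.5, rounded up to 218, and 3 x 218 = 654. The 174 does not. With n = 2(z₁ + z₂)² / d², two-sided alpha 0.017 gives 2(2.387 + 0.842)² / 0.33² = 191.4, so 192 per group. An alpha of 0.025 gives 175. That is a separate sample-size matter. Here it means only that the starting power is already below 80%.

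**Baseline for this check.** 660 x 0.8 / 3 = 176 per arm. Noncentral-t power for 0.33 at two-sided alpha 0.017 is 0.757.

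**Chance of a split.** If the two members are allocated independently, a pair is split between control and a web arm with probability 2 x 1/3 x 2/3 = 4/9. Given that one member is a control, the other is in a web arm with probability 2/3.

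**Dilution.** Let p be the share of participants with a co-enrolled household member and c the fraction of the effect that passes to a control. Both are assumptions; the documents give neither. The model sets any mutual reinforcement between two web-arm partners to zero. The share of the web-versus-control effect lost is p x 2/3 x c, and the remaining effect is 0.33 x (1 - loss).

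| p | c | Loss | Effect left | Power, 176 per arm |
|---|---|---|---|---|
| none | none | 0 | 0.33 | 0.757 |
| 2% | 0.25 | 0.02 x 2/3 x 0.25 = 0.3% | 0.329 | 0.754 |
| 5% | 0.50 | 0.05 x 2/3 x 0.50 = 1.7% | 0.3245 | 0.741 |
| 10% | 1.00 | 0.10 x 2/3 x 1.00 = 6.7% | 0.308 | 0.688 |

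The last row is an extreme bound. It would need 0.10 x 660 = 66 people, or 33 couples, about three couples in every four of 44 practices. It also supposes that a control with no login and no nurse contacts gets the whole effect.

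**The case against.** The strongest reply is that the protocol says nothing false here, and that the problem may hardly arise. A random mailing of up to 100 per practice yielding 15-20 recruits should produce few couples. The partner item was never presented as contamination control; it balances the arms. All of this stands. It limits the size of the point but does not close the route.

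A reader might also infer more than the documents support:

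- **That paired outcomes invalidate an individual-level analysis.** For any two arms, a pair falls together in one of them with probability 2/9 and is split between them with probability 2/9, so the covariance terms cancel in the variance of the difference. Simulations with an assumed within-pair correlation of 0.5 and 10% or 20% of patients co-enrolled gave a type I error of 0.0167 and 0.0170 against a nominal 0.017; a separate simulation gave 0.015-0.016. There is no inflation.
- **That the nurse-versus-minimal contrast is diluted too.** Both arms already use the website. They differ mainly in what is delivered to the patient personally, and the model above says nothing about that contrast.
- **That the bias must always be towards no difference.** A web patient's co-enrolled partner is also in a web arm with probability 2/3, and mutual support could raise the web-arm effect.
- **That family support is the main subject of session 2, or that both web arms are told to involve the spouse.** Session 2 names three sources of support, and the spouse request appears only under the web plus nurse arm.
- **That a control would in practice use the partner's website.** Access is by personal password, and sessions are tailored to the user's own weight and goals.

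**Conclusion.** The gap is real and minor. Neither the entry routes, the exclusions nor the allocation keeps household members out of different arms, and part of the web intervention reaches into the home. The supported consequence is partial exposure of some controls, mainly diluting web versus control.

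On the assumed range of 2-5% co-enrolment and 25-50% transfer, the cost is at most 1.7% of the effect and about 1.6 percentage points of power (0.757 to 0.741). Most of the shortfall from 80% is present before any dilution and should not be attributed to this point. The case for acting is that prevention is cheap and later correction is not possible.

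**What to change.** Add one line to the Exclusions: *another member of the same household already taking part in the trial*. When the invitation list is drawn in each practice, keep one person per address. At screening, ask about household members in the trial beside the partner-in-household item already needed for stratification; this also covers opportunistic referrals.

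The cost is an address check, one question, and a few interested people turned away. With one person refused per pair, 2-5% of 660 is 13-33 participants, or about 7-17 refusals across up to 44 practices. They would need replacing by other invitees, because at the low end of expected recruitment 44 x 15 = 660 is exactly the stated minimum.
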